10.7 Additional Efficacy Analyses

The following additional efficacy endpoints will be summarized for the set of all Arm A subjects in the ITT population and in each of the GT1-infected and GT2-infected groups of the ITT population; within these 3 groups of subjects, the endpoints will also be summarized for the geographic region of China:

- The percentage of subjects with HCV RNA < LLOQ at each post-baseline visit in the DB Treatment Period (using data as observed);
- The percentage of subjects with SVR₄;
- A summary of reasons for SVR₄ non-response (e.g., on-treatment virologic failure, relapse, re-infection, other);
- The percentage of subjects with HCV virologic failure through PT Week 12 (i.e., the SVR₁₂ non-responders due to on-treatment virologic failure or Relapse₁₂);
- The percentage of subjects with SVR₂₄*;
- A summary of reasons for SVR₂₄ non-response (e.g., on-treatment virologic failure, relapse, re-infection, other)*;
- The percentage of subjects who relapsed after achieving SVR₁₂ (**Relapse₂₄**).

* These endpoints will be summarized for the HCV/HIV co-infected subjects (determined at Screening) within the populations/groups identified above.

The following additional endpoints will be summarized for the set of all subjects in the OL Population and for each of the GT1-infected and GT2-infected groups of the OL Population; within these 3 groups of subjects, the endpoints will also be summarized for the geographic region of China:

- The percentage of subjects with HCV RNA < LLOQ at each post-baseline visit in the OL Treatment Period (using data as observed);
- The percentage of subjects with SVR₄;
- A summary of reason for SVR₄ non-response (e.g., on-treatment virologic failure, relapse, re-infection, other);
- The percentage of subjects with SVR₁₂*;
- A summary of reason for SVR₁₂ non-response (e.g., on-treatment virologic failure, relapse, re-infection, other)*;
- The percentage of subjects with SVR₁₂ by HCV genotype and available subtype;

- The percentage of subjects with SVR₁₂ by prior HCV treatment history (treatment-naïve and treatment-experienced, with further breakdown by type of prior HCV treatment experience);
- The percentage of subjects with SVR₁₂ by geographic region;
- The percentage of subjects with HCV virologic failure through PT Week 12;
- The percentage of subjects with SVR₂₄*;
- A summary of reason for SVR₂₄ non-response (e.g., on-treatment virologic failure, relapse, re-infection, other)*;
- The percentage of subjects who relapsed after achieving SVR₁₂ (**Relapse₂₄**).

* These endpoints will be summarized for the HCV/HIV co-infected subjects (determined at Screening) within the populations/groups identified above.

In the above analyses for SVR, HCV virologic failure, and relapse, the number and percentage of subjects with each endpoint among those receiving active treatment during the DB or the OL Treatment Period, as applicable, will be calculated along with a two-sided 95% Wilson score CI. Imputations for missing data will be performed as described in Section 6.3 for analysis of SVR, HCV virologic failure, and relapse. All other endpoints will be presented using data as observed.

As additional endpoints, the secondary endpoints will be summarized for the geographic region of China within the set of Arm A subjects in the ITT population and in each of the GT1-infected and GT2-infected groups of the ITT population.

A summary of the subjects who completed treatment and relapsed (defined as **Relapse_{overall}**) will be prepared displaying the number of subjects relapsing overall and by SVR visit window (within the SVR₄, SVR₁₂, SVR₂₄ windows or after SVR₂₄ window), including the subject number and the SVR visit window corresponding to the first HCV RNA value of those indicating the occurrence of relapse. A similar listing will be prepared for subjects who prematurely discontinued treatment and relapsed after having HCV RNA < LLOQ at their Final Treatment Visit. These summaries will be presented across geographic regions and for the geographic region of China within the set of Arm A

subjects in the ITT population and in each of the GT1-infected and GT2-infected groups of the ITT population as well as within the overall OL population and the GT1-infected and GT2-infected groups in the OL population.

Listings of subject numbers with reason for non-response will be prepared for the SVR endpoints.

The concordance between SVR₁₂ and SVR₂₄ will be assessed by the agreement between SVR₁₂ and SVR₂₄ and the positive predictive value (PPV) and negative predictive value (NPV) of SVR₁₂ on SVR₂₄. The agreement between SVR₁₂ and SVR₂₄ is a percentage defined as the number of subjects achieving both SVR₁₂ and SVR₂₄ and the number of subjects where both SVR₁₂ and SVR₂₄ are not achieved. The PPV of SVR₁₂ on SVR₂₄ is the proportion of subjects who achieve SVR₂₄ out of all subjects who achieved SVR₁₂. The NPV of SVR₁₂ on SVR₂₄ is the proportion of subjects who do not achieve SVR₂₄ out of all subjects who did not achieve SVR₁₂. Similarly, the concordance between SVR₄ and SVR₁₂ will be summarized. These summaries will be presented across geographic regions and for the geographic region of China within the set of Arm A subjects in the ITT population and in each of the GT1-infected and GT2-infected groups of the ITT population as well as within the overall OL population and the GT1-infected and GT2-infected groups in the OL population.

For each additional analysis, a two-sided 95% CI will be produced only if there are at least 10 subjects in the summary.

10.8 HCV and HIV Resistance Analyses

For subjects who enroll in South Korea or Singapore, full length NS3/4A and NS5A from baseline samples will be sequenced by next generation sequencing (NGS). For subjects who enroll in South Korea or Singapore who experience HCV virologic failure (on-treatment HCV virologic failure or post-treatment relapse as defined in Section 10.1), full length NS3/4A and NS5A genes from the first sample after virologic failure with HCV RNA \geq 1000 IU/mL will be sequenced by NGS. For resistance analysis only, the last

sample collected before OL Day 1 will be considered the baseline sample for Arm B subjects. For genotype 1-infected subjects experiencing virologic failure who enroll in China, amino acids 1 – 181 in NS3 and 1 – 215 in NS5A from the baseline sample and the first sample after virologic failure with HCV RNA ≥ 1000 IU/mL will be sequenced by population sequencing. An appropriate subtype-specific prototypic reference sequence will be used for comparison with sequences from samples. Subjects who experience HCV virologic failure will be referred to as subjects in the primary virologic failure (PVF) population, and a listing by subject that includes HCV subtype, IL28B genotype, reason for SVR₁₂ non-response, time point(s) sequenced as closest to time of HCV virologic failure, and HCV RNA value at the HCV virologic failure time point(s) will be produced for these subjects. In addition, all listings described below will display HCV subtype, and reason for SVR₁₂ non-response in the subject identifier for each subject. A separate listing will delineate all subjects in the PVF population for whom no sequencing was performed (e.g., lost to follow-up while HCV RNA ≤ 1000 IU/mL).

Subjects from South Korea and Singapore and GT1-infected subjects from China treated with active study drug who do not achieve SVR₁₂ and who do not meet the above criteria for the PVF population (i.e., prematurely discontinue study drug with no on-treatment HCV virologic failure, have HCV reinfection, are missing SVR₁₂ data or have other reasons as described in Section 10.1, Reasons for SVR₁₂ Non-Response), but have a time point with HCV RNA ≥ 1000 IU/mL after treatment discontinuation, will have the sample at that time point sequenced. For subjects from South Korea and Singapore and GT1-infected subjects from China who are lost to follow-up with less than 6 weeks of therapy while not virally suppressed (e.g., HCV RNA never $<$ LLOQ or have increase in viral load post-nadir), the sample at the latest available time point with HCV RNA ≥ 1000 IU/mL and the corresponding baseline sample will be sequenced. These subjects will be referred to as the non-PVF population. A listing of all subjects in the non-PVF population with post-baseline sequencing available will be created that is similar to the listing of subjects in the PVF population with post-baseline sequencing. For each DAA target, signature amino acid positions and a key subset of amino acid positions are shown

in Table 14. Appropriate subtype-specific prototypic reference sequences will be used for comparison with sequences from samples.

Table 14. List of Signature Amino Acid Positions and a Key Subset of Amino Acid Positions

Target	Signature Amino Acid Positions	Key Subset of Amino Acid Positions
GT1, NS3	36, 43 (GT1a only), 54, 55, 56, 80, 107, 122, 132 (GT1a only), 155, 156, 158, 168, 170, 175 (GT1b only)	155, 156, 168
GT1, NS5A	24, 28, 29, 30, 31, 32, 54 (GT1b only), 58, 62, 92, 93	24, 28, 30, 31, 58, 92, 93
GT2, 4 – 6, NS3	36, 43, 54, 55, 56, 80, 155, 156, 168	155, 156, 168
GT2, 4 – 6, NS5A	24, 28, 29, 30, 31, 32, 58, 62, 92, 93	24, 28, 30, 31, 58, 92, 93
GT3, NS3/4A	36, 43, 54, 55, 56, 80, 155, 156, 166, 168	155, 156, 168
GT3, NS5A	24, 28, 29, 30, 31, 32, 58, 92, and 93	24, 28, 30, 31, 58, 92, 93

Only samples with an HCV RNA level of ≥ 1000 IU/mL will undergo sequence analysis in order to allow accurate assessment of products of amplification. Therefore, if the HCV RNA level at the time of virologic failure or treatment discontinuation is < 1000 IU/mL, the sample closest in time after failure/discontinuation with an HCV RNA level ≥ 1000 IU/mL will be used. Included time points for analyses on samples from subjects who do not achieve SVR₁₂ are 1) the sample closest in time after failure/discontinuation with an HCV RNA level of ≥ 1000 IU/mL, and 2) 24 weeks post-DAA treatment, provided that resistance-associated substitutions were detected at the time of failure/discontinuation.

The following definitions will be used in the resistance analyses by population sequencing:

- Baseline polymorphism: a polymorphism in a baseline sample determined by comparison of the amino acid sequence of the baseline sample to the appropriate prototypic reference amino acid sequence for a given DAA target.

- Post-baseline substitution: an amino acid substitution in a post-baseline time point sample that was not detected at baseline in the subject.

The following definitions will be used in the resistance analyses by NGS:

- Baseline polymorphism: a polymorphism in a baseline sample ($\geq 2\%$ or $\geq 15\%$ prevalence within a subject's viral population depending on frequency threshold utilized) that was not present in the appropriate prototypic reference amino acid sequence for a given DAA target (NS3/4A or NS5A).
- Substitution at signature amino acid position: substitution (relative to reference) present at a detection threshold of $\geq 2\%$ or $\geq 15\%$ (depending on frequency threshold utilized) within a subject's viral population in a baseline or a post-baseline sample at a signature amino acid position.
- Post-baseline substitution: an amino acid substitution in a post-baseline time point sample that was not detected at baseline ($< 2\%$) in the subject and is detectable in $\geq 2\%$ of the sequences from the sample.
- Enriched substitution: substitution present at both baseline and in a post-baseline sample whose prevalence in the post-baseline sample is at least 20 percentage points greater than the prevalence in the baseline sample [(post baseline % – baseline %) ≥ 20].
- Treatment-emergent substitution by NGS: a post-baseline substitution or an enriched substitution.

Analysis will be performed separately for each HCV subtype and treatment duration within each listing.

Analysis 1: The following analyses will be performed for all subjects who enroll in South Korea or Singapore:

- A listing of all baseline polymorphisms ($\geq 2\%$ detection threshold) at signature amino acid positions for each DAA target (NS3 and NS5A) for subjects in the ITT population.
- The number and percentage of subjects with baseline polymorphisms at detection-thresholds of $\geq 2\%$ and $\geq 15\%$ at signature amino acid positions (ITT

population). This table includes prevalence of each baseline polymorphisms and a summary of number of subjects with polymorphisms in NS3 only, in NS5A only, any in NS3, any in NS5A, any in NS3 or NS5A, any in NS3 and NS5A.

- Total number and percentage of subjects with baseline polymorphisms *at the key subset of amino acid positions* in NS3 only, in NS5A only, any in NS3, any in NS5A, any in NS3 or NS5A, any in NS3 and NS5A (ITT population) by genotype, subtype, and total.

Analysis 2: The impact of baseline polymorphisms on treatment outcome will be assessed for **mITT-GT-VF** population for subjects who enroll in South Korea or Singapore as follows: for each polymorphism, the SVR₁₂ rate will be calculated for subjects with and without the polymorphisms and the 2 rates will be compared using Fisher's exact test. Analysis will be grouped by HCV subtype, treatment duration, and DAA target (NS3 or NS5A). The following will be included in the analyses of impact of baseline polymorphisms on treatment outcome:

- Polymorphisms at signature amino acid positions (vs no polymorphisms at that position), using detection thresholds of $\geq 2\%$ and $\geq 15\%$. The analysis will include the number of subjects with polymorphisms in NS3 only, in NS5A only, any in NS3, any in NS5A, any in NS3 or NS5A, any in NS3 + NS5A.
- Each polymorphism at signature amino acid position (vs not that variant) using detection thresholds of $\geq 2\%$ and $\geq 15\%$. The analysis will include the number of subjects with polymorphisms in NS3 only, in NS5A only, any in NS3, any in NS5A, any in NS3 or NS5A, any in NS3 + NS5A.

Analysis 3: In subjects who enroll in South Korea or Singapore, the SVR₁₂ rate will be calculated and compared using Fisher's exact test between subjects with or without polymorphisms at 15% detection threshold in NS3 only, in NS5A only, any in NS3, any in NS5A, any in NS3 or NS5A, any in NS3 and NS5A at the *key subset of amino acid positions*. Analysis will be performed by HCV genotype, subtype, and overall on the mITT-GT-VF population.

Analysis 4: The following analyses will be performed for subjects who enroll in South Korea or Singapore who do not achieve SVR₁₂ (with separate summaries for subjects in PVF and non-PVF populations) and have post-baseline resistance data available:

- Listings by subject of all *treatment-emergent substitutions* relative to the baseline amino acid sequences will be provided for each DAA target (NS3 and NS5A).
- Listings by subject of all *substitutions at signature amino acid positions* in a post-baseline time point for each DAA target (NS3 and NS5A).

Analysis 5: For subjects who enroll in China who experience virologic failure and have sequence data available, the following analyses will be conducted:

- A listing of all baseline polymorphisms at signature amino acid positions for each DAA target (NS3 and NS5A).
- Listings by subject of all post-baseline substitutions relative to the baseline amino acid sequence will be provided for each DAA target (NS3 and NS5A).
- Listings by subject of all emerged substitutions, by amino acid position and substitution within a DAA target in a post-baseline sample relative to the baseline amino acid sequence will be provided for each DAA target (NS3 and NS5A).
- Listings by subject of all post-baseline substitutions at signature amino acid positions relative to the appropriate prototypic reference amino acid sequence will be provided for each DAA target (NS3 and NS5A).

If resistance-associated substitutions are not detected in a given target for a subject at the time of failure/discontinuation, then that target may not be sequenced in subsequent samples from that subject.

HCV Genotype/Subtype

Phylogenetic analysis will be conducted on HCV sequence from all available baseline samples from subjects who enroll in South Korea or Singapore and genotype 1-infected

subjects experiencing virologic failure who enroll in China in order to accurately determine subtype.

Subjects' HCV genotype and subtype may be assessed based on the Inno-LiPA 2.0 Assay used by the Central lab (Covance), the HCV genotype determination by Sanger sequencing a region of NS5B by the Central lab (Covance) and/or from phylogenetic analysis of the full length NS3/4A, and/or NS5A sequences performed by AbbVie. If the phylogenetic analysis is available, then it will be used to determine the subject's HCV genotype and subtype. If it is not available, then the Sanger sequencing assay result will be used to determine the subject's HCV genotype and subtype, if available. Finally, if neither the phylogenetic analysis result nor the Sanger sequencing assay results is available, then the Inno-LiPA assay results will be used to categorize the subject. This subtype information will be presented in summaries of efficacy subgroup analyses. The baseline characteristic summary will use the results from the central laboratory (Sanger sequencing or Inno-LiPA 2.0 Assay [if Sanger sequencing not available]).

A summary of HCV genotype subtype as provided by the central laboratory (Sanger sequencing or Inno-LiPA 2.0 Assay [if Sanger sequencing not available]) versus phylogenetic analysis also will be provided.

HIV Drug-Resistance Analyses

If any subject on stable HIV-1 ART develops a confirmed, quantifiable plasma HIV-1 RNA level (HIV-1 RNA \geq 200 copies/mL at one assessment and \geq 500 copies/mL on repeat testing) after starting the study, the HIV-1 protease, reverse transcriptase and/or integrase sequences, as applicable, will be analyzed by Monogram Biosciences using the GenoSure[®] Prime drug resistance assays for subjects from South Korea and Singapore. The number of subjects who demonstrate HIV genotypic resistance and the genotypic resistant mutations detected in the samples obtained from these subjects will be tabulated and summarized in the final CSR, as applicable. Resistance will be defined as described by the IAS-USA Panel.⁹

10.9 Patient Reported Outcomes

The following instruments will be used to collect patient reported outcomes (PROs): EuroQol-5 Dimensions-3 Level (EQ-5D-3L) and Fatigue Severity Scale (FSS).

Subject's responses to the EQ-5D-3L will be combined into a unique health state using a 5-digit code with 1 digit from each of the 5 dimensions. The EQ-5D-3L states will be converted into a single preference-weighted health utility index score by applying weights.^{10,11} The VAS score will be analyzed separately. For EQ-5D-3L index and VAS scores, no imputation will be performed for missing items.

The FSS measures the impact of fatigue over the past week on specific types of functioning. The survey consists of 9 questions using a 7-point Likert scale. A total score is calculated as the average of the individual item responses (adding up all the answers and dividing by nine). Higher FSS scores indicate a higher degree of impact of fatigue. Imputation will be applied to the total score as described in Section 6.3.

Summary statistics (n and mean,) at each protocol-specified visit and for change from baseline (n, mean, SD, minimum and maximum) to each protocol-specified visit will be provided for the EQ-5D-3L health index score and VAS score and for the FSS total score for each treatment arm in the ITT population (as applicable). For each of these scores, mean change from Baseline to the final scheduled DB Treatment Period Visit (Week 8 or Week 16) will be compared between treatment arms using an analysis of covariance (ANCOVA) model with treatment arm as a factor and baseline score as a covariate.

The number and percentage of subjects who have ever experienced an increase from baseline up through each applicable time point of greater than or equal to 0.7 in the FSS total score will also be calculated for each treatment arm in the ITT population (as applicable), along with two-sided 95% CIs based on the normal approximation to the binomial distribution. In addition, percentages of subjects meeting the criteria at each applicable time point during the DB Treatment Period will be compared between Arm A and Arm B using Fisher's Exact Test.

If a subject starts another treatment for HCV, then all PRO values for this subject measured on or after the start date of the new HCV treatment will be excluded from analyses.

The analyses described above will also be performed for the geographic region of China.

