#### **EuroQol-5 Dimensions-3 Level (EQ-5D-3L)**

The EQ-5D-3L is a health state utility instrument that evaluates preference for health status (utility). The 5 items in the EQ-5D-3L comprise 5 dimensions (mobility, self-care, usual activities, pain/discomfort, and anxiety/depression) each of which are rated on 3 levels of severity. Responses to the 5 items encode a discrete health state which is mapped to a preference (utility) specific for different societies. Subjects also rate their perception of their overall health on a separate visual analogue scale (VAS). The EQ-5D-3L should require approximately 5 minutes to complete.

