### **8.1.3 Patient Reported Outcomes**

The handling of missing data for patient reported outcomes (PROs) will be as follows. The missing items of the FSS questionnaire will be imputed with the average score of the answered items as long as more than 50% of the items on the FSS are answered. For EQ-5D-3L index and VAS scores, no imputation will be performed for missing items.

The mean change from baseline will be summarized descriptively for the FSS total score and the EQ-5D-3L health index score and VAS score for each treatment arm. For each of these scores, mean change from Baseline to the final scheduled DB Treatment Period Visit (Week 8 or Week 16) will be compared between treatment arms using an analysis of

covariance (ANCOVA) model with treatment arm as a factor and baseline score as a covariate.

The cumulative number and percentage of subjects who have ever experienced an increase from baseline in the FSS total score of greater than or equal to 0.7 through each applicable timepoint will also be calculated for each treatment arm.

The analyses described above will also be performed separately for each geographic region. Additional analyses of PROs will be performed as useful and appropriate.

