### 8.3 Randomization Methods

The randomization will be stratified by geographic region (China, Singapore, South Korea), genotype (GT1, GT2, combined GT3 – 6), and HCV/HIV co-infection status (co-infected, not co-infected). In China, eligible subjects will be randomized to Arm A or Arm B in the following ratios: 2:1 for GT1, 2:1 for GT2, and 2:1 for combined GT3 – 6. In Singapore and South Korea, eligible subjects will be randomized to Arm A or Arm B in the following ratios: 2:1 for GT1 and 2:1 for GT2.

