5.2 Variables Used for Stratification of Randomization

Randomization of subjects will be stratified by geographic region (China, Singapore and South Korea), genotype (GT1, GT2, combined GT3 – 6), and HCV/HIV co-infection status (yes, no).

If a subject was randomized based on incorrect stratification information, the correct stratification information (if known at the time of the primary SVR₁₂ analysis) will be used to define subpopulations for analyses.

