10.5.2 Assessment of Homogeneity Across Stratification Variables

Heterogeneity across the randomization stratification variables of geographic region, genotype, and HCV/HIV co-infection status will be examined for the primary efficacy

endpoint of SVR₁₂ in Arm A using the chi-square test of homogeneity. The 14 strata are presented in Section 10.5.

If heterogeneity across the randomization stratification is detected, a confidence interval for the primary endpoint based on the 14 strata will be created using a stratum weighted variance calculated using the equations below. The variance of p_s will be estimated by:

$$Var(p_s) = \sum_{h=1}^H w_h^2 \frac{p_h(1-p_h)}{n_h - 1}$$

and the 2-sided 95% CI will be calculated as $p_s \pm z\sqrt{Var(p_s)}$, where z is the $1-\alpha/2$ point of the standard normal distribution. Note that n represents the number of subjects in Arm A within the ITT population, n_h represents the number of subjects in stratum h , w_h will be estimated by n_h/n , p_h = the proportion of subjects achieving SVR₁₂ in stratum h , and p_s = the proportion of subjects with SVR₁₂ among n subjects which can be defined as:

$$p_s = \sum_{h=1}^H w_h p_h$$

Using the equations above, a confidence interval for the SVR₁₂ rate across all 14 strata will be presented, along with the number and percentage (p_h) of subjects achieving SVR₁₂ within each of the 14 strata.

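### The between-arm PRO ANCOVA leaves out the randomisation strata, so it is mildly conservative to the extent that region, genotype group or HIV status predicts PRO change beyond the baseline score

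*SAP*

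**What the plan says.** SAP 5.2 states that randomisation is "stratified by geographic region (China, Singapore and South Korea), genotype (GT1, GT2, combined GT3 – 6), and HCV/HIV co-infection status (yes, no". Protocol 8.3 lists the same three factors ("The randomization will be stratified by geographic region (China, Singapore, South Korea" and so on). Allocation is 2:1 in each genotype group of each country. Not every combination exists, because GT3–6 subjects are recruited only in China. SAP 10.5.2 therefore counts 14 cells ("The 14 strata are presented in Section 10.5").

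For the FSS total, EQ-5D-3L index and VAS scores, SAP 10.9 has mean change from baseline to the final double-blind visit "compared between treatment arms using an analysis of covariance (ANCOVA) model with treatment arm as a factor and baseline score as a covariate". Protocol 8.1.3 specifies the same model ("covariance (ANCOVA) model with treatment arm as a factor and baseline score as a covariate"), and the synopsis agrees. SAP 12.1 lists one change to the PRO section, about the wording of the FSS increase summary, and adds no stratum term.

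A second between-arm PRO comparison concerns FSS increases of at least 0.7: "percentages of subjects meeting the criteria at each applicable time point during the DB Treatment Period will be compared between Arm A and Arm B", by Fisher's exact test without strata.

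The strata do appear elsewhere in the SAP, but only for SVR12 within Arm A: summaries by stratum (10.5), and a homogeneity test with a stratum-weighted interval if heterogeneity is found (10.5.2).

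**The concern.** When allocation is balanced within strata, differences between strata largely cancel out of the comparison of arms. The true sampling error of the treatment difference is then smaller than under simple randomisation. An ANCOVA without the strata does not know this: it counts between-stratum variation as noise and reports too large a standard error. Intervals are then wider than they need be, and a real difference is a little more likely to be missed.

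The strata could matter here for two reasons, although the documents prove neither.

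- **Region.** The protocol's description of the EQ-5D-3L notes that "Responses to the 5 items encode a discrete health state which is mapped to a preference (utility) specific for different societies", and the trial spans three countries.
- **Genotype.** The final double-blind visit is Week 8 for most subjects but Week 16 for treatment-experienced GT3 subjects. Part of the genotype grouping is therefore tied to when the change is measured.

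At stake is the precision of a randomised, double-blind comparison with placebo. No confirmatory claim is at stake.

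**Working it through.** **Plan's own figure.** The documents state no standard deviation, effect size, standard error or power for any PRO comparison, so there is nothing to reproduce.

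**Inputs from the documents.** Two-sided alpha is 0.05 (Protocol 8.1). Stratum sizes come from SAP Table 1, whose arm totals are 336 and 168, together 504. The factors are those of SAP 5.2.

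**Assumed inputs.** R² is the share of the residual variance left after the baseline score that the strata explain; it is shown as a range. The South Korea to Singapore split is taken as 120 to 24 of the 144 regional subjects (5:1). Block sizes of 3 and 6 are both tried, since the documents state none.

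**Formulas.** With the strata balanced by design, the true variance of the arm difference is (1 − R²) times the variance the planned model reports. Hence:

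- reported SE / true SE = 1/√(1 − R²)
- actual two-sided alpha = 2[1 − Φ(1.96/√(1 − R²))]

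Example at R² = 5%: 1/√0.95 = 1.026, and 1.96 × 1.026 = 2.011, which gives an alpha of 4.43%.

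**Check by simulation.** 6,000 null trials were run per setting, with 504 subjects and 2:1 permuted blocks within strata. The planned ANCOVA was compared with one that adds stratum indicators. The Monte Carlo standard error of a 5% rejection rate is √(0.05 × 0.95/6000) = 0.28 points.

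| R² | SE ratio (formula) | Actual alpha (formula) | Simulated alpha, planned model (blocks of 3; 6) | Simulated alpha, strata added (blocks of 3; 6) |
|---|---|---|---|---|
| 0% | 1.000 | 5.00% | 5.50%; 5.02% | 5.48%; 4.93% |
| 2% | 1.010 | 4.77% | 4.83%; 4.75% | 5.10%; 4.87% |
| 5% | 1.026 | 4.43% | 4.48%; 4.38% | 4.93%; 4.97% |
| 10% | 1.054 | 3.88% | 3.73%; 3.97% | 4.72%; 5.10% |
| 20% | 1.118 | 2.84% | 2.97%; 2.87% | 4.68%; 5.25% |

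At R² = 10% the planned model reports a mean SE of about 0.095, against an actual spread of 0.090 to 0.091. With strata added, the reported SE is 0.090.

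**Power.** These runs assume a true effect of 0.265 residual SD, chosen so that the planned model has about 80% power, with blocks of 6 and 4,000 trials each. Power without and with strata:

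- R² = 0%: 81.2% and 81.0%
- R² = 5%: 80.1% and 81.4%
- R² = 10%: 80.4% and 83.2%
- R² = 20%: 81.8% and 87.7%

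**Main effects instead of all cells.** A separate simulation of 4,000 trials per setting added only region, genotype group and HIV status as main effects. At R² of 2%, 5% and 10%, null rejection was 4.6%, 4.4% and 4.1% for the planned model, and 4.7%, 4.9% and 5.3% with the factors added. Power rose by 0.5, 1.6 and 2.6 points. The simpler model is therefore enough when stratum effects are roughly additive.

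**The case against.** The strongest objection is that nothing in the documents shows the strata to be prognostic for PRO change. The EQ-5D-3L sentence describes the instrument in general. SAP 10.9 says only that weights are applied, not that they differ by country, and the FSS and VAS use no societal weights. A fixed difference in level between regions is largely absorbed by the baseline score.

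The larger values of R² would also need sizeable differences. China supplies 360 of 504 subjects, a fraction of 0.714. If China versus the rest carried the whole effect, R² = 0.714 × 0.286 × d² = 0.204d². R² of 2%, 5% or 10% then requires a baseline-adjusted gap d of about 0.31, 0.49 or 0.70 SD. Genotype could add something. HIV status can add little, with at most 50 co-infected subjects and fewer now expected (SAP 12.1). All of this stands. It makes the point conditional and favours the lower end of the range.

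A reader might also infer stronger things that the documents do not support:

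- **That the standard errors are too large whatever the data.** At R² = 0 they are not.
- **That the China-only PRO analysis throws away 144 of 504 subjects.** SAP 10.9 performs it in addition to the full analysis, and SAP 12.1 says the regulator requires analyses of the China subset.
- **That the PROs are among the few randomised comparisons in the trial.** Adverse events, laboratory values and vital signs are also compared between arms (SAP 11.2.2, 11.3.2, 11.4.2), likewise without strata.
- **That the PRO model departs from a stratified convention used for efficacy.** The SAP's stratum analyses of SVR12 are all within Arm A, and the primary interval itself ignores the strata.
- **That the Fisher test on FSS increases must become a stratified test.** No gain was calculated for that change, and it would give up an exact test where cells are sparse.

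Finally, the PROs lie outside the study objectives and the fixed testing sequence, no power is claimed for them, and Protocol 8.1.3 already permits further PRO analyses. That limits the importance of the point but is no reason to keep the less precise model.

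**Conclusion.** The point holds in conditional form. The PRO ANCOVA omits factors that the randomisation balances, and any resulting error is conservative. The standard error, and so the width of the interval, is overstated by about 1%, 3% or 5% if the strata explain 2%, 5% or 10% of the residual variance, and not at all if they explain none. The actual alpha is then about 4.8%, 4.4% or 3.9%. The cost is a little precision and, at those shares, roughly half a point to three points of power where the planned model has about 80%.

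These sizes rest on an assumed R², an assumed split between South Korea and Singapore, and assumed block sizes. The direction does not depend on the last two. The estimated treatment difference is unbiased with or without the strata, there is no excess of false positives, and no primary or secondary conclusion changes. This is an optional improvement that costs almost nothing.

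**What to change.** In SAP 10.9, and in Protocol 8.1.3 if it is amended for other reasons:

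- Add region (China, Singapore, South Korea), genotype group (GT1, GT2, GT3–6) and HCV/HIV co-infection status as main-effect factors to each PRO ANCOVA, using the corrected stratum information that SAP 5.2 already provides for.
- Use main effects and not the 14 cells, several of which will be very small or empty.
- State that the HIV factor will be dropped if very few co-infected subjects enrol.
- Report the adjusted mean difference with its 95% CI.

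Keep the China-only analysis, and leave the Fisher test on FSS increases of at least 0.7 unchanged.

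The cost is a few words and 2 + 2 + 1 = 5 residual degrees of freedom out of about 500. It needs no new data and no further subjects. If the strata turn out not to matter, almost nothing is lost: simulated power at R² = 0 was 81.0% with strata and 81.2% without. The terms are better written into the SAP than left to the protocol's general allowance for extra PRO analyses. Assignments are unblinded subject by subject at the end of the double-blind period, and covariates chosen after that are harder to defend.
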